[Appendix 3](#) (Data collection tool [eCRF] differences pre- and post-protocol amendment 2) details the differences in data collection pre- and post-protocol amendment 2. For variables that were only collected and recorded for patients enrolled pre-amendment 2 (N = 14) relevant data will be presented in by-patient data listings only and no further details with regards to these variables are included in the subsequent sections.

[Appendix 4](#) (Data collection tool [eCRF] differences pre- and post-protocol amendment 3) details the differences in data collection pre- and post-protocol amendment 3.

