2.7 Analysis sets

Assignment of patients to the different analysis sets detailed below will be performed prior to the unblinding of the treatment code and start of the primary analysis.

All enrolled analysis set: All enrolled patients who provided informed consent (as recorded in the Informed consent eCRF), will be deemed as the all enrolled set, as such, accounting for all enrolled patients. Patients who are re-screened and randomized will be counted only once, based on their re-screening record. Patients who are re-screened but who eventually are not randomized will also be counted once. Enrolled patients, who were not randomized (with the exception of patients re-screened and subsequently randomized) will be sorted last as part of a “Not Randomized” treatment group in by-patient data listings based on the all enrolled analysis set. Linked records will be sorted together using patient numbers and informed consent date (to order chronologically).

The following analysis sets are defined for primary and final update analysis purposes as detailed in this RAP:

Randomized analysis set: All randomized patients, regardless of whether the patient received study drug. This set will consist of all patients who provided informed consent (as recorded in the Informed consent eCRF) with a randomization number and a completed randomization date as per IRT.

Safety (SAF) analysis set: The SAF analysis set will consist of all patients who received at least one infusion of study drug. Patients will be analyzed according to the treatment actually received. If a patient received only part of the infusion (i.e. study drug infusion permanently discontinued), the patient will be regarded as having received study drug infusion and will be assigned to the SAF analysis set. At least one infusion, or part of an infusion (as recorded in the Dosage administration record – infusion eCRFs) will be used to assign patients to the SAF analysis set.

Full analysis set (FAS): The FAS will consist of all randomized patients who received at least one infusion of study drug. Patients who are randomized due to erroneous use of the IRT system and who did not receive at least one infusion of study drug will be excluded from the

FAS. Following the intent-to-treat principle, patients will be analyzed according to the treatment they were assigned to at randomization.

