The following subsets of patients will be identified for inclusion in the proposed primary and secondary efficacy sensitivity analyses ([Section 2.10.1](#) [Analysis of the primary efficacy variable] and [Section 2.10.2](#) [Analysis of secondary efficacy variables], respectively):

- Total LBM Week 24 Completers FAS Analysis Subset: Patients who have a windowed visit Week 24 total LBM assessment (kg) (primary endpoint) having completed treatment (Week 24 [EOT]).
- SPPB Week 24 Completers FAS Analysis Subset: Patients who have a windowed visit Week 24 SPPB assessment (secondary efficacy endpoint) having completed treatment (Week 24 [EOT]).
- Gait speed Week 24 Completers FAS Analysis Subset: Patients who have a windowed visit Week 24 gait speed assessment (secondary efficacy endpoint) having completed treatment (Week 24 [EOT]).
- SPPB Week 48 Completers FAS Analysis Subset: Patients who have a windowed visit Week 48 SPPB assessment (secondary efficacy endpoint) having completed both the treatment (Week 24 [EOT]) and post-treatment follow-up (Week 48 [EOS]).
- Gait speed Week 48 Completers FAS Analysis Subset: Patients who have a windowed visit Week 48 gait speed assessment (secondary efficacy endpoint) having completed both the treatment (Week 24 [EOT]) and post-treatment follow-up (Week 48 [EOS]).

Per Protocol (PP) analysis set: The PP analysis set will include all FAS patients without major deviations from the protocol procedures at the time of the primary analysis. Major protocol deviations and the definition of the PP analysis set will be identified and finalized based on blinded review of the data, prior to the data extraction for the primary analysis and unblinding of the treatment code.

Modified Per Protocol (PP) analysis set: The Modified PP analysis set will include all FAS patients without a major deviation from the protocol procedures occurring after Week 24 and will be used at the time of the final update analysis. Major protocol deviations and the definition of the modified PP analysis set will be identified and finalized, prior to the data extraction for the final update analysis.

For the definitions of major protocol deviations see [Section 3.10](#) (Protocol deviations).

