2.10.1.3 Statistical model, hypothesis, and method of covariate analysis

The primary efficacy objective of the study is to show that at least one bimagrumab treatment group (bimagrumab 700 mg and/or bimagrumab 210 mg) will increase total LBM (kg) (change from Baseline) compared to placebo at Week 24 by rejecting the null hypothesis described below at significance level $\alpha=0.05$ level (two-sided):

$$H_0: \mu_T = \mu_P \text{ versus } H_1: \mu_T \neq \mu_P$$

where μ_T and μ_P are the mean change from Baseline in total LBM (kg) at Week 24 for bimagrumab treatment groups (bimagrumab 700 mg, bimagrumab 210 mg) and placebo treatment group respectively.

A mixed model repeated measures (MMRM) will be used to test the hypothesis with change from Baseline at all windowed post-baseline visits (Week 12 and Week 24) as response variable, and treatment group, visit, region (Japan/Non-Japan), treatment date (early/late) and Baseline total LBM (kg) as covariates (see “Covariates” column of Table 2.2 [[Section 2.6](#) {Subgroups}]).

In addition, the following four interaction terms will be fitted:

Treatment group*visit.

Region*visit.

Treatment date*visit.

Baseline total LBM*visit.

An unstructured within patient correlation structure will be used for the covariance matrix. The Kenward-Roger approximation will be used to estimate denominator degrees of freedom. Residual/restricted maximum likelihood (REML) method will be used to estimate parameters. The total LBM (kg) will be transformed by using natural logarithm prior to calculating the change from Baseline and performing any analysis. The covariate, Baseline total LBM (kg) will also be log transformed. The antilog of the point estimate and associated 95% confidence interval of the treatment difference will be computed prior to presentation. The two-sided p-value for the exponential (exp) least squares mean, $\exp(\text{LSM})$, ratio (%) between each of the two bimagrumab treatment groups and placebo at Week 24 and at Week 12 will be reported. The Holm-Bonferroni method will be used to adjust the Type I error for the two comparisons

(bimagrumab 700 mg versus placebo and bimagrumab 210 mg versus placebo) treatment group at Week 24. No control for multiplicity will be made at Week 12. Although not part of the formal hypothesis testing, the two-sided p-value for the LSM difference between “Active Total: Efficacy” and placebo at Week 24 and at Week 12 will also be reported.

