2.10.1.4 Handling of missing values/censoring/discontinuations

The above analysis will be performed using all available data under the assumption that the probability of missing values of total LBM (kg) are independent of unobserved assessments (missing at random [MAR]). Therefore, the missing values will not be imputed for the primary analysis.

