3.4 Definition of Baseline and post-baseline assessments

Baseline (derived) is defined as the last available assessment (scheduled or unscheduled) prior to the start of the first infusion of study drug, including pre-dose assessments at Day 1. All Day 1 assessments are to be performed prior to the start of the first infusion of study drug with the exception of DXA assessments. The protocol allows a + 2-day window for performing Baseline DXA. Dual energy X-ray absorptiometry (DXA) assessments obtained within the allowed 2-day window following the first infusion of study drug at Day 1 will still be regarded as Baseline assessments.

Assessments performed after the start of the first infusion are considered post-baseline assessments with the exception of DXA assessments, as specified above.

Change from Baseline is derived where both Baseline and post-baseline values are available:

Change from Baseline = (post-baseline value – Baseline value).

Percentage (%) change from Baseline at each post-baseline visit:

Percentage (%) change from Baseline = $(\text{[post-baseline value – Baseline value]}/\text{Baseline value}) \times 100$.

End of Treatment (derived) is defined as the last available assessment (scheduled or unscheduled) assigned to treatment (expected per protocol at Week 20 + 56-days).

End of Study (derived) is defined as the last available assessment (scheduled or unscheduled) assigned to the study.

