	End of Study (derived)	End of Study is defined as the last available assessment (scheduled or unscheduled) assigned to the study.		

[figure not shown]
* For pre-amendment 2 patients, cut-off at Week 20 + 56 days. ** For patients who discontinued during treatment epoch, the target visit day values are EOT (derived) + 168 days at Week 48.

Table 3.4 Echocardiography (only for patients enrolled)/X-ray assessment of surgical procedure

Study Epoch	Visit Name	Target Visit Day	Start Day of Visit Window	End Day of Visit Window
Screening	Screening	Day -39 to -1		
Treatment	Baseline	Defined as the last available assessment (scheduled or unscheduled) prior to the start of the first infusion of study drug, including pre-dose assessments at Day 1.		

	Week 24	Day 168	1	Last infusion of study drug + 56 days *
	End of Treatment (derived)	End of Treatment is defined as the last available assessment (scheduled or unscheduled) assigned to treatment and including the 56-days *.		
Post-treatment follow-up	Week 36	252 **	1 day after last infusion of study drug + 56 days *	Target visit day + 42 days
	Week 48	336 **	295 **	Last known date in study
	End of Study (derived)	End of Study is defined as the last available assessment (scheduled or unscheduled) assigned to the study.		

X-ray assessment: At Screening local X-ray taken during or after surgery is to be used. If bone union is incomplete at Week 24 per central reading, X-rays need to be performed until this is achieved at Week 36 and potentially Week 48 as well * For pre-amendment 2 patients, cut-off at Week 20 + 56 days. ** For patients who discontinued during treatment epoch, the target visit day values are EOT (derived) + 84 days and EOT (derived) + 168 days for Week 36 and Week 48, respectively. In addition, for the discontinued patients, the start day of the Week 48 visit name is 1 day after last infusion of study drug + 56 days (for pre-amendment 2 patients, cut-off at Week 20) + 126 days.

[figure not shown]

Table 3.7 DXA

Study Epoch	Visit Name	Target Visit Day	Start Day of Visit Window	End Day of Visit Window
Treatment	Day 1	Day 1 to 3	1	3
	Baseline	Defined as the last available assessment (scheduled or unscheduled) prior to the start of the first infusion of study drug, including pre-dose assessments at Day 1 (+ 2-day window).		
	Week 12	Day 84	4	126
	Week 24	Day 168	127	Last infusion of study drug + 56 days *

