	End of Treatment (derived)	End of Treatment is defined as the last available assessment (scheduled or unscheduled) assigned to treatment and including the 56-days *.		

* For pre-amendment 2 patients, cut-off at Week 20 + 56 days. DXA assessment: The protocol allows a + 2-day window for performing Baseline DXA. Dual energy X-ray absorptiometry (DXA) assessments obtained within the allowed 2-day window following the first infusion of study drug at Day 1 will still be regarded as Baseline assessments.

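### The Week 24 DXA window closes at each patient's own last infusion plus 56 days, so missing only the Week 20 dose can remove an on-schedule scan from the primary analysis

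*SAP*

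**What the plan says.** Table 3.7 DXA in SAP 3.5.1 has two post-baseline windows: Week 12 (Days 4-126) and Week 24 (from Day 127). The Week 24 window ends at "Last infusion of study drug + 56 days". Its footnote reads "For pre-amendment 2 patients, cut-off at Week 20 + 56 days", and SAP 2.3 counts 14 such patients. The table has no later DXA window.

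The primary model (SAP 2.10.1.3) takes "change from Baseline at all windowed post-baseline visits (Week 12 and Week 24) as response variable". SAP 2.10.1.4 states that "The above analysis will be performed using all available data", under missing at random and without imputation. For the full analysis set, SAP 2.7 says: "Following the intent-to-treat principle, patients will be analyzed according to the treatment they were assigned to at randomization".

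On the protocol side:

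- Section 5.5.5 permits interruptions and requires treatment to stop only after two missed doses.
- Section 6 keeps later visits on the calendar set by the first dose after a delayed or missed visit. The tolerance is 4 days either way for Weeks 4-12 and 7 days either way for Weeks 16-24.
- Section 5.5.9 places the End of Treatment visit of a patient who stops treatment about 28 days after the last dose, or at once if the patient has already been off drug for longer.

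**The concern.** The window opens on a study day but closes on a dosing day. A patient who receives the Week 20 infusion has ample room. A patient who misses only that infusion, stays in the study and attends Week 24 within the permitted days may have a valid scan that fits no analysis visit. Whether an observed primary value counts then depends on adherence after randomisation. That sits badly with the promise to use all available data and with the intent-to-treat principle.

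When only Week 20 is missed, the scans at risk are those 57-70 days after the last dose. Protocol 3.3 reports that the muscle-volume effect of a single 10 mg/kg dose lasted about one month in healthy volunteers. Protocol 6.4.5 reports LBM returning to baseline after drug withdrawal. The imputation analysis in SAP 2.10.1.5 itself assumes a diminishing effect after study discontinuation. Setting such scans aside under missing at random would therefore, if anything, favour bimagrumab.

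The planned checks would not reveal it:

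- The completers subset consists of "Patients who have a windowed visit Week 24 total LBM assessment (kg) (primary endpoint) having completed treatment", so it needs a windowed value.
- The imputation analysis would treat the scan as missing and replace it.
- The per-protocol analysis uses the same windows.

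**Working it through.** **Inputs.** Target days: Week 12 = 84, Week 16 = 112, Week 20 = 140, Week 24 = 168 (Protocol Table 6-1; SAP Table 3.1). With the Protocol section 6 tolerances, Week 12 falls on Days 80-88, Week 16 on 105-119, Week 20 on 133-147 and Week 24 on 161-175. Window end = last infusion day + 56.

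**The plan's own window starts.** Midpoint + 1 day: DXA Week 24 = (84 + 168)/2 + 1 = 127, as in Table 3.7 DXA. Table 3.1 Week 24 = (140 + 168)/2 + 1 = 155, as stated.

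**Week 20 given.** An infusion on Day 133, 140 or 147 closes the window on Day 189, 196 or 203. No scan on Days 161-175 is lost.

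**Only Week 20 missed.** The last infusion is Week 16. The planned gap is 168 - 112 = 56 days; the permitted range is 161 - 119 = 42 to 175 - 105 = 70 days. Gaps of 57-70 days are lost.

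| Week 16 infusion | Window closes | Permitted scan days lost |
|---|---|---|
| Day 105 | Day 161 | 162-175 (14 of 15) |
| Day 108 | Day 164 | 165-175 (11 of 15) |
| Day 112 | Day 168 | 169-175 (7 of 15) |
| Day 115 | Day 171 | 172-175 (4 of 15) |
| Day 119 | Day 175 | none |

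Over all pairs: 14 + 13 + ... + 1 + 0 = 105 of 15 x 15 = 225. A scan on Day 168 exactly is lost for 7 of the 15 Week 16 days (105-111). On the exact schedule, Days 112 and 168, nothing is lost.

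**Weeks 16 and 20 both missed.** The last infusion is Week 12, so the window closes between Day 80 + 56 = 136 and Day 88 + 56 = 144. If the End of Treatment scan is done at the missed Week 20 visit (Days 133-147), it is too late in 11 + 10 + ... + 3 = 63 of 9 x 15 = 135 pairs.

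**Reach.** The rule applies to at least 3 x 70 - 14 = 196 of the 210 patients planned for the tested arms. This is how many the rule covers, not how many would lose a scan.

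**Possible bias.** Let p be the share of an active arm with such scans and f the fraction of a 1.0 kg effect that has faded in them. Using all scans, the estimate is (1 - p) x 1.0 + p x (1 - f) x 1.0; dropping them gives about 1.0. The difference is p x f x 1.0 kg. The documents give neither p nor f. For assumed p of 2%, 5% and 10%, full fading gives 0.02, 0.05 and 0.10 kg; half fading gives 0.01, 0.025 and 0.05 kg.

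**Power.** Two-sample t-test, 1.0 kg, SD 1.0 kg, two-sided alpha 0.025: above 99.9% at 70 per arm (the plan states 99%), 99.9% at 60 and 99.8% at 54.

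**The case against.** **The anchor may be nominal.** SAP 3.4 describes End of Treatment as the last assessment "assigned to treatment (expected per protocol at Week 20 + 56-days"), and similar wording recurs in SAP 2.3, 2.9.2, 2.11.1 and 2.11.7. If Week 20 itself were the anchor, the problem would vanish. But the fuller form in SAP 2.3 and 2.11.1 still names the last infusion; the parenthesis only says when that infusion is expected. A special Week 20 cut-off for pre-amendment 2 patients would also be unnecessary if it applied to all. SAP 3.5.1 further says that the last treatment window ends with the last assessment assigned to treatment, but the table defines that assignment by the same 56 days, so this is circular. What stands is that the wording needs reconciling on either reading.

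**A patient who misses the last dose may count as having discontinued.** End of Treatment would then fall near Day 140, inside the window. Such patients are indeed unaffected. But Protocol 5.5.5 makes discontinuation mandatory only after two missed doses, and section 6 keeps the calendar after a missed visit.

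**The direction of bias is uncertain.** This has force. The muscle-volume data are from single doses in healthy volunteers, and the SAP's fading assumption concerns patients who leave the study. Protocol 6.4.5 also describes an LBM plateau at 8-12 weeks after a single 30 mg/kg dose, which covers the 57-70 days at issue, though at a higher dose than here. Full fading is therefore an upper bound.

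**Few patients may be affected.** Protocol 6.3 expects full compliance unless visits are missed, and an affected patient's Week 12 value still enters the model. Both points limit the size of the problem but do not remove it.

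**Conclusion.** The concern holds. As written, Table 3.7 DXA can exclude a protocol-compliant Week 24 scan solely because the Week 20 dose was missed: 105 of 225 permitted day pairs, and 63 of 135 when Weeks 16 and 20 are both missed and End of Treatment is done at the Week 20 visit. A single earlier missed dose, or an End of Treatment visit about 28 days after the last infusion, is unaffected.

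The number of patients concerned cannot be derived from the documents. The possible overstatement of 0.02-0.10 kg against a 1.0 kg target rests on assumed shares of 2-10% and complete fading. Power is not at stake. The defect is one of principle and of an ambiguous primary dataset, and it is cheap to remove. It should be corrected before unblinding, because a primary-endpoint window chosen afterwards would be open to challenge.

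**What to change.** For DXA and total LBM, end the Week 24 window on one fixed study day for all patients. Day 196 (planned Week 20, Day 140, + 56) matches the cut-off already used for pre-amendment 2 patients and loses 0 of the 225 pairs. State that Week 24 LBM is used regardless of doses received, and align the wording of SAP 3.4 and 3.5.1 with this. Keep last infusion plus 56 days for treatment-emergent safety. Run the current windowing as a sensitivity analysis and report, by arm, how many scans it removes.

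The sponsor should also confirm which window table governs SPPB and gait speed, since some tables are not visible in the public SAP. If it is Table 3.1, the same fixed end day should apply, with Week 36 starting the next day.

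The cost is one table cell and its programming; no new data are needed. There are two downsides. Some Week 24 values could come from patients well past their last dose: up to 196 - 112 = 84 days after a Day 112 infusion and 196 - 84 = 112 days after a Day 84 infusion. Scans on Days 197-203 after a Week 20 dose given on Days 141-147 would no longer count, but those lie outside the protocol's Days 161-175.

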3.6 Handling of missing values/censoring/discontinuations

In general, unless otherwise specified, no data imputation will be performed for the missing values.

3.7 Imputation of missing and incomplete dates

Adverse event and concomitant medication dates will be imputed per the Novartis standard tables, listings and figures (TLFs) conventions as detailed in the RAP Module 8 (Programming Specifications). All missing or incomplete dates shall however be listed in by-patient data listings as recorded in the eCRF.

3.8 Clinically notable values

Clinically notable criteria will be used to identify notable abnormalities of key laboratory tests, vital signs values and ECG intervals.

Table 3.6 Clinically notable laboratory values, vital signs, ECG intervals and echocardiography

Laboratory Assessments	
Hemoglobin	< 8.0 g/dL
Hemoglobin	< LLN
Glycated hemoglobin (HbA1C)	≥ 7.5%
Average blood glucose (based on fasting values only)	≥ 9.0 mmol/L
Platelet count	< 75 x 10 ⁹ /L
Estimated GFR*	< 30 mL/min
Total bilirubin concentration	> 1.5 x ULN
Total serum bilirubin	> 1.6 mg/dL (27 µmol/L)
ALT	> 3 x ULN (see Table 3.7 [Liver event and laboratory trigger definitions] for more clinically notable values)
AST	> 3 x ULN (see Table 3.7 [Liver event and laboratory trigger definitions] for more clinically notable values)
ALP	> 3 x ULN (see Table 3.7 [Liver event and laboratory trigger definitions] for more clinically notable values)
Total CK	> 3 x ULN
Sodium (Na)	> ULN < LLN
Testosterone, male patients	> ULN
Testosterone, female patients	> ULN
Albumin	< LLN
Pre-albumin	< LLN
Magnesium	< LLN
BUN	< LLN
Uric acid	< LLN
Lipase	> 2 x ULN
Amylase	> 2 x ULN

Lipase	≥ 3 x ULN	
Amylase	≥ 3 x ULN	
Lipase and/or amylase	≥ 3 x ULN	
Vital Signs		
	Low	High
Systolic blood pressure (mmHg)	< 90 mmHg or decrease from Baseline of ≥ 20 mmHg	> 150 mmHg, > 180 mmHg, or increase from Baseline of ≥ 20 mmHg
Diastolic blood pressure (mmHg)	< 50 mmHg or decrease from Baseline of ≥ 15 mmHg	> 90 mmHg, > 100 mmHg, or increase from Baseline of ≥ 15 mmHg
Pulse rate (bpm)	< 60 bpm or decrease from Baseline of ≥ 15 bpm	> 100 bpm or increase from Baseline of ≥ 15 bpm
Weight (kg)	≥ 5% decrease from Baseline	
ECG		
QTcF**	≥ 450 msec for males ≥ 460 msec for females ≥ 500 msec	
QTc	> 30 msec change from Baseline or > 60 msec change from Baseline	
PR	> 250 msec	
ECHO		
	Low	High
Left ventricular ejection fraction (%)	- ≥15% decrease in ejection fraction from Baseline - Decrease in ejection fraction to a value less than 45%	
Interventricular septum thickness(mm), measured at end-diastole		- > 15mm septum thickness - ≥ 50% increase in thickness from Baseline
Left ventricular posterior wall thickness (mm)		- > 15mm wall thickness - ≥ 50% increase in thickness from Baseline

ALT: Alanine aminotransferase. AST: Aspartate aminotransferase. ALP: Alkaline phosphatase. BUN: Blood urea nitrogen. CK: Creatine kinase. LLN: Lower limit of normal. MDRD: Modification of Diet in Renal Disease ECG: Electrocardiogram. ECHO: Echocardiography. GFR: Glomerular filtration rate. HbA1C: Glycated hemoglobin. PR: Period from the beginning of the P wave until the beginning of the onset of ventricular depolarization. QT: Interval time from the start of the Q wave to the end of the T wave. ULN: Upper limit of normal.* Estimated GFR using Modification of Diet in Renal Disease (MDRD) equation. **QT interval with Fredericia correction.

